Neurotrophic keratitis develops due to VZV affecting the sensory nerves and causing hypoesthesia, which leads to the deterioration of corneal epithelium and a punctate keratopathy. If the epithelial breakdown progresses, large corneal epithelial defects occur. Sterile corneal ulcerations occur that may also become secondarily infected. If untreated, the cornea may become opaque, progressively thin, and may eventually perforate.

For the purposes of our study, we define zoster dendrite as a stuck-on rod shaped or branching lesion without terminal bulbs and not a corneal melt, keratouveitis, sclerouveitis, or corneal erosion related to neurotrophic keratitis.

Ganciclovir ophthalmic gel

Ganciclovir ophthalmic gel 0.15% was approved by the Food and Drug Administration (FDA) in September 2009 for the treatment of acute herpetic keratitis (dendritic ulcers). The results of three pooled phase II studies and one phase III trial demonstrated similar cure rates of ganciclovir ophthalmic gel 0.15% compared to acyclovir ophthalmic ointment 3% at day 7. Ganciclovir ophthalmic gel 0.15% demonstrated non-inferiority compared to acyclovir ophthalmic ointment 3%. Of note, acyclovir ophthalmic ointment is not commercially available in the United States and there are no head-to-head clinical trials of ganciclovir ophthalmic gel compared to trifluridine 1% ophthalmic solution for the treatment of acute herpetic keratitis. Ganciclovir ophthalmic gel 0.15%, has not been studied in patients with stromal keratitis.

Previous trials have shown that topical antivirals have been ineffective in the treatment of herpes zoster keratitis. However, there have been a few unpublished reports of use of Zirgan for herpes zoster keratitis (http://www.revoptom.com/content/c/24774/).

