Ganciclovir ophthalmic gel has minimal systemic absorption, with the total daily topical dose approximately 0.04% and 0.1% of oral and intravenous ganciclovir doses, respectively. Rapid penetration of ganciclovir has been demonstrated within 5 minutes with topical administration resulting in therapeutic drug levels in ocular tissue, which is imperative for the treatment of herpetic keratitis. ¹⁴

Ganciclovir ophthalmic gel 0.15% is FDA approved for the treatment of acute herpetic keratitis (dendritic ulcers). ^{13,15} This study looks at the use of ganciclovir gel for the treatment of zoster keratitis. Current available topical antiviral alternatives are trifluridine 1% ophthalmic solution and vidarabine ointment (VIRA-A Ophthalmic Ointment). Our study will provide data regarding the use of ganciclovir ophthalmic gel as an additional tool in the treatment of herpes zoster keratitis which can have potentially blinding sequelae.

Genteal Gel

Genteal gel is a non-prescription eye lubricant gel and is commonly used for treatment of dry eye, irritated eyes. There is no anti-viral agent within genteal gel.

Oral anti-viral

Acyclovir and valacyclovir are the standard treatments used in patients with herpes zoster¹⁷ to prevent long-term complications, including intraocular complications. Acyclovir and valacyclovir have not been studied as single use treatments of herpes zoster dendrites.

II. Hypothesis

We hypothesize that ganciclovir ophthalmic gel 0.15% will be an effective treatment of herpes zoster dendritic keratitis as measured by reduction of the dendritic ulcer by 90% within 2 weeks in at least 50% of subjects receiving ganciclovir while on oral anti-viral therapy compared with 0% of subjects receiving placebo while on oral anti-viral therapy.

III. Study Objectives

The purpose of this study is to evaluate the efficacy (defined as the reduction in ulcer size by 90%) of topical ganciclovir 0.15% in treatment of herpes zoster dendritic keratitis.

The investigators will enroll 33 patients with a diagnosis of HZO with corneal involvement. Their medical records will be reviewed, including their demographic data as well as ophthalmic and medical histories. Subjects will be recruited from the Department of Ophthalmology at Northwestern University (NU), as well as from the qualified practices of physician members of the Chicago Cornea Association and selected cornea practices nationwide.

IV. Study Population

A. Inclusion Criteria

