- 1. Males and Females, age 18 and above who have been diagnosed with a corneal infection caused by the herpes zoster virus
- 2. Have not been on ganciclovir gel or any other form of topical antiviral therapy for the past month
- 3. Able and willing to attend subsequent follow-up visits

B. Exclusion Criteria

- 1. Associated retinitis
- 2. Patients with a known allergy to hypromellose gel, ganciclovir, acyclovir, or valacyclovir
- 3. Patients who will require systemic or intra-vitreal ganciclovir therapy
- 4. Patients who are pregnant or breastfeeding

V. Study Procedures

A. Study Design

This is a prospective, randomized, parallel group study with two arms: subjects receiving oral anti-virals as standard of care therapy while receiving either ganciclovir ophthalmic gel 0.15% (Zirgan) or a placebo ointment (genteal gel). Subjects with corneal dendritic involvement from herpes zoster will be randomized (1:1) to receive ganciclovir ophthalmic gel 0.15% gel or placebo, which will be applied to the affected eye 5 times a day for 7 days, followed by 3 times a day for an additional 7 days. At two weeks, if the zoster dendrite has not healed, rescue therapy can be performed at

the discretion of the treating physician (Zirgan, the study drug, will not be used as a rescue therapy).

Clinical examinations including a dilated fundus examination will be performed at the Screening/Baseline Visit. Subsequent clinical examinations will be performed at study visits 1, 2, and the End of Study/Early Termination Visit, however, fundus examinations are not completed at subsequent examinations. Two sets of slit lamp photographs will be obtained at each visit.

Slit-lamp photographs can be obtained with fluorescein or Rose Bengal staining; however the same staining method should be used throughout the study. Photos will first be taken without fluorescein or Rose Bengal and then taken with fluorescein or Rose Bengal. Time to reduction ulcer size will be recorded as the primary end point and compared among the two groups from the slit lamp photographs. Slit lamp photographs will be reviewed by a qualified physician, who will be masked to the patient information and the study drug received. Intraocular pressure (IOP) measurement will be performed at each study visit and subjects will receive numbing eye drops prior to the IOP.

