In order to obtain reliable safety and efficacy data, it is critical that each subject complies with the dosing schedule specified in this protocol. Each subject will be given a dosing diary to fill out every time they apply the study drug or placebo. Subjects must also continue with the intake of their systemic medications prescribed.

D. Randomization and Masking

We anticipate enrollment of 33 patients. The study groups will be assigned in a 1:1 ratio, with expected non-completion rate of 10% this will give us 15 patients per treatment group. Neither the patient nor the study doctor or study staff will be able to pick which study group the patient is in or know which study group the patient is in. If subjects have an infection in both eyes, only on eye will be randomized to receive either Zirgan or placebo. The other eye will be given standard of care treatment.

Subjects will be randomized to receive ganciclovir gel (Zirgan®) versus hypromellose gel (Genteal Gel®; Placebo) to be applied topically. A computer algorithm for random number generation will be used to generate the treatment assignments. The study is double-masked and all site investigators, study staff, and subjects will be masked to the group to which subjects are randomized. Masked study doctors at Northwestern University will be reading all slit lamp photos, including those from the other participating sites. The study staff that will be dispensing the study drug and placebo will also be masked.

E. Rescue Therapy

Rescue therapy is defined as any treatment that would have a therapeutic effect on the herpes zoster keratitis. Rescue therapy will be offered if progressive corneal thinning, corneal inflammation, or worsening of the dendritic keratitis occurs. All uses of rescue therapy will be deemed medically necessary by the site investigator.

If rescue therapy is needed after a subject has treatment failure, the site investigator must report the treatment failure and the type of rescue therapy used to the lead site. The lead site study staff can be reached by calling [contact].

VI. Risks and Benefits

A. Risks

Ganciclovir ophthalmic gel 0.15%

Most common adverse reactions reported in patients were blurred vision (60%), eye irritation (20%), punctate keratitis (5%), and conjunctival hyperemia (5%). ¹⁶

Dilated fundus examination

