The dilation medicine will cause some minor stinging after being placed in the eye. The dilation will cause light sensitivity and blurry vision for 4-6 hours.

Slit lamp photography

Bright flashes may cause discomfort to the subject.

Intraocular pressure (IOP) measurement

Numbing eye drops (proparicaine 0.5% ophthalmic solution) will be used prior to taking subject's intraocular pressure. These eye drops may cause redness and stinging. During the measurement, the study doctor will use a machine that touches the surface of the eyes. In rare circumstances, this machine could scratch the subjects' cornea. Such scratches are usually self-heal in less than 24 hours.

The potential harm to the subjects is loss of privacy and confidentiality. Indirect identifiers will be used to link data obtained from different methods. The key will be stored separately from the data and will be destroyed after data collection has been completed.

B. Benefits

Subjects' herpes zoster keratitis may get better as a result of the use of ganciclovir gel. The knowledge gained from this study may benefit future patients with this condition.

VII. Statistical Considerations

A. Sample Size Justification

We will recruit 33 patients in order to account for drop-out or non-completion rate of 10%, providing approximately 15 patients per treatment group.

With 15 patients per group we have sufficient power to test H:p1=p2 vs H1: p1>p2 with type 1 error of 5%, when true values of p1=55% and p2=5%. See below.

Two Independent Proportions (Null Case) Power Analysis Numeric Results of Tests Based on the Difference: P1 - P2 H0: P1-P2<=0. H1: P1-P2=D1>0. Test Statistic: Fisher's Exact test

Sar	nple	Sample	Prop H1	Prop				
	Size	Size	Grp 1 or	Grp 2 or	Diff	Diff		
G	rp 1	Grp 2	Trtmnt	Control	if H0	if H1	Target	Actual
Power	N1	N2	P1	P2	D0	D1	Alpha	Alpha
]	Beta							
0.9978	30	30	0.5500	0.0500	0.0000	0.5000	0.0500	0.0022

B. Statistics

We will use descriptive statistics to present the data in a convenient fashion, including graphics. Success rates in two treatment groups will be compared using Fisher's Exact test. 95% Confidence intervals for rates in each of the treatment groups will also be provided.

VIII. Ethical Considerations

A. Data Disclosure and Subject Confidentiality

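### Does the plan need a written rule for scoring patients who are rescued before Week 2 and then heal?

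*Combined protocol and SAP*

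**What the plan says.** Section II (Hypothesis) gives the only success criterion with a time window: "reduction of the dendritic ulcer by 90% within 2 weeks". It makes no exception for rescue. Section VII.B (Statistics) says "Success rates in two treatment groups will be compared using Fisher's Exact test" and does not mention rescue.

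Rescue appears in two places. Section V.A (Study Design) says "At two weeks, if the zoster dendrite has not healed, rescue therapy can be performed", at the treating physician's discretion and not with the study drug. Section V.E (Rescue Therapy) says "Rescue therapy will be offered if progressive corneal thinning, corneal inflammation, or worsening of the dendritic keratitis occurs". It defines rescue broadly, as any treatment that acts on the keratitis.

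Section V.E also sets a reporting duty. It opens with "If rescue therapy is needed after a subject has treatment failure" and says that the site investigator "must report the treatment failure and the type of rescue therapy used to the lead site". A date is not listed. Section V.C (Subject Compliance) describes the diary: "Each subject will be given a dosing diary to fill out every time they apply the study drug or placebo". The visit schedule in V.A has a medical history and an eye examination at every visit, including Weeks 1 and 2.

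**The concern.** Take a patient who worsens in the first week, receives rescue, and shows a 90% reduction at Week 2. Section II, read literally, counts a success. Section V.E associates rescue with failure of treatment, which suggests a non-success, but it does not define that failure or connect it with the success count. Section VII.B does not choose between the two.

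With 15 patients per arm, one or two classifications can matter. If the rule were chosen after unmasking, the verdict could depend on a choice that nobody wrote down. The required rescue report and the dosing diary also leave it unclear how an analyst would know when rescue began.

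**Working it through.** **1. What each scoring rule needs**

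- Rule B, success regardless of rescue: only the masked reading of the photographs up to Week 2. No rescue information is needed.
- Rule A, rescued before the Week 2 photograph counts as non-success: only whether rescue came before that photograph. The report to the lead site gives the fact and type of rescue, and the Week 1 and Week 2 histories can place it in time. An exact date would help but is not a precondition.

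**2. Whether the two sections conflict**

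Section II states an outcome criterion. The V.E sentence is conditional: it says what a site must report if rescue follows a failure. It assigns no score and does not say that every rescued patient has failed. Read with VII.B, the plan therefore has a default, which is Rule B. Sections V.A and V.E can be read as two separate triggers, non-healing at two weeks and worsening at any time. How they fit together is for the sponsor to reconcile, and no clinical rule is suggested here.

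**3. The plan's own power figure**

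Inputs from VII.A: p1 = 0.55, p2 = 0.05, one-sided Fisher's exact test, alpha 0.05. Exact enumeration over two binomials gives 0.9978 at 30 per arm, which matches the table. At the 15 per arm in the text it gives 0.901, the base used below. The difference between 30 and 15 is a separate matter.

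**4. Effect of Rule B on power**

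Assume that a share r of non-responders is rescued before Week 2 and that a share h of those reaches 90% reduction. The documents give neither. With the same r and h in both arms:

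- p1* = 0.55 + 0.45rh and p2* = 0.05 + 0.95rh
- difference = 0.50 − 0.50rh = 0.50(1 − rh)
- expected patients affected = 15 × (0.45 + 0.95) × rh = 21rh

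| r, h | p1*, p2* | Patients affected, of 30 | Power, both arms | Power, placebo only converts | Power, ganciclovir only converts |
|---|---|---|---|---|---|
| 5%, 20% | 0.5545, 0.0595 | 0.21 | 0.883 | 0.878 | 0.906 |
| 10%, 20% | 0.559, 0.069 | 0.42 | 0.864 | 0.853 | 0.910 |
| 10%, 50% | 0.5725, 0.0975 | 1.05 | 0.810 | 0.774 | 0.922 |

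**5. Effect of Rule A on power**

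Rule A has its own cost, because some would-be responders may be rescued first. If 5% or 10% of them are, in both arms, the success rates are multiplied by 0.95 or 0.90, and power is 0.879 or 0.853. At low rates the two rules cost about the same.

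**6. How often the two rules disagree**

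Exact enumeration with similar conversion in both arms and no would-be responder rescued:

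| r, h | Only A significant | Only B significant | Total |
|---|---|---|---|
| 5%, 20% | 0.0224 | 0.0038 | 0.026 |
| 10%, 20% | 0.0438 | 0.0066 | 0.050 |
| 10%, 50% | 0.1021 | 0.0111 | 0.113 |

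If 5% of would-be responders are also rescued first, the totals are 0.052, 0.071 and 0.123.

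**7. Type I error if the better rule is picked afterwards**

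With equal true rates from 0.05 to 0.6, and (r, h) from (0.1, 0.2) to (0.3, 0.7), the chance that at least one rule is significant is at most 0.036. That is below the 5% in VII.A.

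**8. One patient re-scored**

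The planned rates give about 8/15 (0.55 × 15 = 8.25) and 1/15 (0.05 × 15 = 0.75), with one-sided p = 0.007. Scoring one rescued placebo patient as a success gives 8 against 2 and p = 0.025, still significant. Two such patients give 8 against 3 and p = 0.064.

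**The case for a change.** The strongest case is that a trial of 30 evaluable patients has little room for an unstated rule. Section V.E lets rescue be any effective treatment, so h could be high. The remark in the background section that "topical antivirals have been ineffective in the treatment of herpes zoster keratitis" covers only topical antivirals and does not settle the matter. If 10% of all placebo non-responders were rescued and healed (rh = 0.10) while ganciclovir stayed at 0.55, p2 would be 0.05 + 0.95 × 0.10 = 0.145, and power under Rule B would fall to 0.64. Re-scoring two placebo patients can reverse a result, and with a two-sided test the single re-scoring in step 8 moves p from 0.014 to 0.0502. Section V.A also names time to reduction in ulcer size as the primary end point, and rescue is not addressed there either.

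Part of this stands. The plan is silent, and a sentence on rescue with a date on the report would make it tidier. But the 0.64 rests on a rate with no source and on conversion in the placebo arm alone. It also describes the power of one valid rule, not an error in the test. The two-sided p carries little weight because VII.A states a one-sided alternative, although VII.B does not repeat it. The silence on the time end point is the same gap, and analysts can fill it in the same way.

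**Conclusion.** No change to the plan is called for. This is a missing detail that analysts can fill sensibly: score by the masked photographs up to Week 2, as Section II says, and show the result with rescued patients counted as non-successes beside it. Either rule gives a valid comparison, and which should be primary is a fair trade-off.

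Under the assumed rates, about 0.2 to 1 of 30 patients is affected. Power under the default is 0.88 to 0.81, against 0.90, when conversion is similar in both arms. The rules disagree in 2.6% to 11.3% of trials, or up to 12.3% if some would-be responders are also rescued, with the upper end at h = 50%. Type I error stayed at or below 0.036 in the null cases tried.

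The conclusion rests on early rescue followed by healing being uncommon, which the documents neither state nor contradict. If it proved common, mainly on placebo, the choice of rule would weigh more.

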Both groups will receive the standard 7-day oral therapy of acyclovir (800 mg po five times daily), valacyclovir (800 mg po five times daily), or valacyclovir (1000 mg po three times daily). This oral anti-viral treatment is being given as standard treatment for herpes zoster to prevent long-term complications, including intraocular complications. If the treating physician feels strongly about an altered dosing regimen, this is allowed as long as it is reported. A topical steroid will not be administered unless there is associated inflammation.

	Screening/ Baseline Visit (Week 0)	Study Visit 1 (Week 1)	Study Visit 2 (Week 2)	End of Study Visit/Early Termination Visit (Week 3)		
Informed consent	X					
Medical history	X	X	X	X		
Dilated fundus examination	X					
Eye exam	X	X	X	X		
IOP	X	X	X	X		
Slit lamp photos	X	X	X	X		
Oral antiviral dispensed	X					

Study drug dispensed	X			
Diary reviewed		X	X	

The study drug will be sent to the study doctor in a sealed container that should be opened by the patient at home. Patients will be required to fill out a dosing diary. The dosing diary and the remaining drug must be returned to the NU study site from all participating sites.

A Coded Identifier List (CIL) will contain the subject's name, subject's medical record number, subject's date of birth, and the Study ID Number assigned by the study staff. The CIL will be stored on a secure server, be password protected, and will be maintained by authorized study personnel. Once a subject has been given a Study ID Number, all data collected will be identified through this Study ID Number. Each site will maintain their own Coded Identifier List and Northwestern University will not have access to each site's CIL.

B. Study Drug

Ganciclovir ophthalmic gel 0.15%: Sufficient quantity for 15 eyes. The subjects will put the study drug into affected eye(s) 5 times a day while awake for 7 days, followed by 3 times a day while awake for 7 days, or until healing of corneal ulcer. Clinical examinations will be performed at the Screening/Baseline Visit and study visits 1, 2, and the End of Study/Early Termination Visit.

The drug and placebo will be randomized and distributed to the participating centers that will not have access to the drug by Northwestern University study staff. The study drug will be stored and maintained by the Department of Ophthalmology at Northwestern Memorial Hospital located at [name].

C. Subject Compliance

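### Section VII.A claims sufficient power with 15 patients per group, but its only power figure (0.9978) is for 30 per group; at 15 the same one-sided test gives about 0.90

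*Combined protocol and SAP*

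**What the plan says.** Section VII.A (Sample Size Justification) makes the claim in words: "With 15 patients per group we have sufficient power to test H:p1=p2 vs H1: p1>p2 with type 1 error of 5" per cent, for true rates of 55% on ganciclovir and 5% on placebo. It then points to a power table for Fisher's exact test. The table's hypotheses are one-sided: "H0: P1-P2<=0. H1: P1-P2=D1>0. Test Statistic". Its single data row reads N1 = 30, N2 = 30, P1 = 0.55, P2 = 0.05, target alpha 0.05, power 0.9978. No other power value, and no target power, appears in the document.

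The planned size is consistent everywhere else:

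- Section III (Study Objectives): "The investigators will enroll 33 patients with a diagnosis of HZO with corneal involvement".
- Section V.B (Study Drug), on the ganciclovir supply: "Sufficient quantity for 15 eyes".
- Section V.D (Randomization and Masking), on 1:1 allocation: "with expected non-completion rate of 10% this will give us 15 patients per treatment group".
- Section VII.A itself: "We will recruit 33 patients in order to account for drop-out or non-completion rate of 10%, providing approximately 15 patients per treatment group".

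Two related statements matter here. Section VII.B (Statistics) says "Success rates in two treatment groups will be compared using" Fisher's test, without giving a side. Section II (Hypothesis) expects success in at least half of the ganciclovir group, "compared with 0% of subjects receiving placebo while on oral anti-viral therapy".

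**The concern.** The sentence and the table that is meant to support it describe different trials. The table is the only evidence for the power claim, and it is for 60 evaluable patients where the plan expects about 30. A reader or ethics committee who takes 0.9978 as this trial's power would think a false negative almost impossible and the design nearly insensitive to its assumptions. Neither holds at 15 per group.

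The side of the test is a smaller matter, but at this size it can decide the result, so Section VII.B should not leave it to inference.

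**Working it through.** **Inputs.** From Section VII.A: p1 = 0.55, p2 = 0.05, alpha = 0.05, Fisher's exact test, upper one-sided alternative. Group size is 30 (table row) or 15 (text of VII.A, V.D).

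**Formula.** Let a be the number of successes among n1 on ganciclovir and b the number among n2 on placebo. The one-sided Fisher p-value is P(X ≥ a), where X is hypergeometric: n1 drawn from n1 + n2 patients, of whom a + b are successes. Power is the sum, over all (a, b) with p ≤ 0.05, of Bin(a; n1, p1) × Bin(b; n2, p2).

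**Step 1: the plan's own figure.** With n1 = n2 = 30 the sum is 0.9978, which matches the table to four decimals. The two-sided version at 30 per group gives 0.9945. The row is therefore a correct one-sided calculation for 30 in each group. It is not a calculation for 30 in total with a wrong label. The trailing 0.0022 is 1 − 0.9978, that is, beta.

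**Step 2: the planned size, n1 = n2 = 15.** For each placebo count b, find the smallest a that reaches p ≤ 0.05. Then multiply the probability of b by the probability of at least that a.

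| b on placebo | smallest significant a | p-value | P(b) at 5% | P(≥ a) at 55% | product |
|---|---|---|---|---|---|
| 0 | 4 | 0.0498 | 0.4633 | 0.9937 | 0.4604 |
| 1 | 6 | 0.0400 | 0.3658 | 0.9231 | 0.3376 |
| 2 | 8 | 0.0251 | 0.1348 | 0.6535 | 0.0881 |
| 3 | 9 | 0.0302 | 0.0307 | 0.4522 | 0.0139 |
| 4 | 10 | 0.0328 | 0.0049 | 0.2608 | 0.0013 |
| 5 | 11 | 0.0328 | 0.0006 | 0.1204 | 0.0001 |

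Before rounding the products sum to 0.9013, and larger b add nothing visible. Type II error is 1 − 0.9013 = 0.0987, against 1 − 0.9978 = 0.0022 for the tabulated size.

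**Step 3: the number of completers.** 33 × 0.90 = 29.7. With 29 completers the one-sided power is 0.900 (15 ganciclovir, 14 placebo) or 0.899 (14 and 15), so about 0.90 holds either way.

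**Step 4: if the test in VII.B is two-sided.** At 55% vs 5% and alpha 0.05:

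| ganciclovir / placebo | two-sided power |
|---|---|
| 15 / 15 | 0.820 |
| 15 / 14 | 0.832 |
| 14 / 15 | 0.865 |
| 17 / 16 | 0.892 |
| 16 / 17 | 0.916 |

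Power can rise as patients are lost because the test is discrete. The last two rows assume that all 33 patients are analysed, which the plan does not say. As an example of the side deciding the result, 4/15 against 0/15 gives p = 0.0498 one-sided and 0.0996 two-sided, while 5/15 against 0/15 is significant either way (two-sided p = 0.0421).

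**Step 5: the rates in Section II.** At 50% vs 0% and 15 per group, one-sided power is 0.982. The rates in VII.A are thus the less favourable pair, and the difference between the sections does not inflate the stated power.

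**Step 6: sensitivity (an assumption, not a figure from the plan).** If the placebo rate were 10% and ganciclovir stayed at 55%, one-sided power would be 0.98 at 30 per group but 0.77 at 15. The table's size hides how much the answer depends on the placebo rate.

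**The case against.** The strongest reply is that the written claim is true. The protocol says only that power is sufficient, sets no target, and never says in words that 15 per group gives 0.9978. The row is openly labelled 30 and 30, so 0.2% is not stated as this trial's type II error. On the plan's own test, rates and alpha, 15 per group gives 0.90, which most would accept. All of this stands. It limits the point to wrong support for an acceptable sample size, but it does not remove it: the text cites the table as its evidence, and nothing in the document shows the power at 15 per group.

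On the side of the test, VII.A declares a one-sided alternative and VII.B follows directly with the same test, so the natural reading is one-sided. That is fair. Naming the side in VII.B is a clarification, not the repair of a contradiction. It is also fair that 0.82 belongs to exactly 15 per group and is the lowest of the nearby splits examined.

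On the rates, at least 50% is compatible with 55%, and the difference is 50 percentage points in both sections. That point is editorial.

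**Conclusion.** The concern holds. The only power figure in the plan, 0.9978, is correct for 30 per group and does not apply to this trial. At the planned 15 per group the same one-sided 5% Fisher test has power of 0.901, or about 0.90 with 29 completers. The chance of missing the planned effect is therefore about 10%.

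This rests on the plan's own rates of 55% and 5% and on the one-sided alternative in VII.A. It does not show an underpowered trial. The sample size can be defended, but its stated justification is wrong and should be corrected. How 30 came to be entered for each group cannot be determined from the document. The unstated side in VII.B and the different rates in Section II are secondary and did not cause the error.

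**What to change.** 1. In VII.A, replace the table row with N1 = N2 = 15 and state power of about 0.90 for the one-sided 5% Fisher test at 55% vs 5%.
2. In VII.B, name the same side as VII.A. If a two-sided test is intended, state power of 0.82 and say that it applies to exactly 15 per group, or give the range over likely splits (0.82 to 0.87 for 29 or 30 completers).
3. Add one sentence explaining why VII.A uses 55% and 5% when Section II gives at least 50% and 0%, or align the two.

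The cost is protocol wording only. Enrolment of 33, 1:1 allocation, 15 per group and Fisher's test are unchanged. The one drawback is a less favourable stated power: about 0.90, or 0.82 if two-sided, in place of 0.998.

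### Cheap improvement: at about 15 per arm Fisher's exact test is valid but conservative, and naming Boschloo's exact test in VII.B would raise one-sided power from 0.901 to 0.949 at VII.A's rates

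*Combined protocol and SAP*

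**What the plan says.** The analysis is set out in VII.B: "Success rates in two treatment groups will be compared using" Fisher's exact test. VII.B does not say whether the test is one- or two-sided. VII.A does: its alternative is that the ganciclovir rate exceeds the placebo rate, "with type 1 error of 5%, when true values of p1=55% and p2=5"%. Its power output is also one-sided and names Fisher's exact test. The expected size in VII.A is 33 recruits with 10% non-completion, "providing approximately 15 patients per treatment group".

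Two other places bear on the point.

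- Section II gives different rates from VII.A: "at least 50% of subjects receiving ganciclovir while on oral anti-viral therapy compared with 0% of subjects receiving placebo".
- Section III speaks of a success criterion, to "evaluate the efficacy (defined as the reduction in ulcer size by 90"%, whereas V.A says: "Time to reduction ulcer size will be recorded as the primary end point".

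No unconditional exact test is mentioned anywhere in the plan.

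**The concern.** Fisher's test conditions on the total number of successes. With about 15 patients per arm few p-values are attainable, so the test usually cannot come close to its nominal level. The part of the 5% that is not used is power given away. In a trial of this size a single extra success in the rejection boundary matters: 5/15 against 1/15, or 7/15 against 2/15, would be reported as not significant, although another exact test at the same 5% level rejects in both. What is at stake is some avoidable risk of a negative result. The validity of the plan is not in question.

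**Working it through.** **Inputs.** Test: Fisher's exact (VII.A, VII.B). Level: 5% one-sided (VII.A). Rates: 55% vs 5% (VII.A) and 50% vs 0% (section II). Completers: 33 × 0.9 = 29.7, so about 15 per arm. Because 15/15 is not guaranteed, I assume 13 plausible splits, written ganciclovir/placebo: 14 to 17 per arm, 28 to 33 in total, arms differing by at most 2.

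**Method.** All tables (x₁, x₂) are enumerated. Power is the sum over rejected tables of Bin(x₁; n₁, p₁) × Bin(x₂; n₂, p₂). Size is the largest such sum over a common rate p₁ = p₂. Boschloo's test takes the one-sided Fisher p-value as its statistic and uses the largest cutoff that keeps the size at or below 5%.

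**Step 1: the plan's own figure.** One-sided Fisher at 30/30, 55% vs 5%, gives 0.9978, as printed in VII.A. That row is for 30 per group. At 15/15 the same calculation gives 0.901.

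**Step 2: type I error at 15/15.** Fisher's maximum is 2.16% (2.1 to 3.1% over the 13 splits). Boschloo's cutoff on the Fisher p-value is 0.0843, with maximum size 4.95%. As this cutoff is above 0.05, every table that Fisher rejects is also rejected by Boschloo. The same holds at all 13 splits.

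**Step 3: the boundary at 15/15.** With no placebo successes both tests need 4 on ganciclovir; Fisher's p for 4 vs 0 is C(15,4)/C(30,4) = 1365/27405 = 0.0498. With 1, 2 or 3 placebo successes Fisher needs 6, 8 or 9 and Boschloo 5, 7 or 8. The one-success gap is also present at 4 to 8 and at 10 placebo successes, but those tables add little at a 5% placebo rate. Two examples:

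- 5/15 vs 1/15: Fisher (3003 × 15 + 5005)/593775 = 0.084; Boschloo 0.0495.
- 7/15 vs 2/15: Fisher 0.054; Boschloo 0.0275.

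**Step 4: power at 15/15, 55% vs 5%.** Fisher 0.9013, Boschloo 0.9495, a gain of 4.8 points. By table: 5 vs 1 gives 1.88, 7 vs 2 gives 2.22, 8 vs 3 gives 0.62, 9 vs 4 gives 0.09 and 10 vs 5 gives 0.01. The sum is 4.82, of which 1.88 + 2.22 = 4.10 comes from the first two.

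**Step 5: power at 50% vs 0%.** At 15/15 both tests need 4 vs 0, so both have P(X ≥ 4 | 15, 0.5) = 1 − 576/32768 = 0.982. At 15/14, Fisher's p for 4 vs 0 is 1365/C(29,4) = 1365/23751 = 0.057, so Fisher needs 5 successes and has power 1 − 1941/32768 = 0.941. Boschloo still rejects at 4 and has 0.982.

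**Step 6: other splits** (Fisher → Boschloo, one-sided 5%; seven of the 13 shown)

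| Ganciclovir/placebo | 55% vs 5% | 50% vs 0% |
|---|---|---|
| 14/14 | 0.875 → 0.933 | 0.971 → 0.971 |
| 14/15 | 0.899 → 0.945 | 0.971 → 0.971 |
| 15/14 | 0.900 → 0.935 | 0.941 → 0.982 |
| 15/15 | 0.901 → 0.949 | 0.982 → 0.982 |
| 16/16 | 0.918 → 0.950 | 0.962 → 0.989 |
| 16/17 | 0.937 → 0.971 | 0.989 → 0.989 |
| 17/16 | 0.922 → 0.966 | 0.976 → 0.994 |

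Over all 13 splits the gain at 55% vs 5% is 2.9 to 5.7 points. At 50% vs 0% it is zero at seven splits and 1.8 to 4.2 points at the other six.

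**The case against.** The strongest reply is that nothing here is broken. Fisher's test is valid, is the same in VII.A and VII.B, is familiar to clinical readers, and has about 90% one-sided power at 15/15 under the plan's own assumptions. A reader might infer that the plan is underpowered or that its test is wrong. The documents support neither, and the point is offered as an improvement only.

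Second, at the planned size the gain vanishes under section II's own rates. Most of the 55% vs 5% gain comes from tables with ganciclovir success of 33% and 47%, below the 50% in the hypothesis. Both statements are correct and limit the benefit. Two stronger readings do not follow, however. One is that Boschloo's test helps under the hypothesis at 15/15; it does not. The other is that it can help only when placebo has successes; that holds at 15/15 but fails at six of the 13 splits, 15/14 among them.

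Third, refining this test may be premature while V.A names a time end point as primary. That stands, and the recommendation is conditional for this reason. VII.B promises a comparison of success rates in any case, so the choice of test for it can be settled now.

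Fourth, the side is already clear from VII.A. Largely so; repeating it in VII.B is a clarification.

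**Conclusion.** The point holds as an optional, low-cost improvement. At one-sided 5% and 55% vs 5%, Boschloo's test gains 4.8 points of power at 15/15 and 2.9 to 5.7 points over the assumed splits, and it never loses a rejection that one-sided Fisher would make. At 50% vs 0% it gains nothing at 15/15 and at most 4.2 points at any of the splits. The figures rest on the one-sided 5% level in VII.A, on independent binomial outcomes, and on the assumed range of completers. They do not depend on the 30-per-group row printed in VII.A. Confidence in the arithmetic is high. Whether the gain is worth a less familiar test is a matter of judgement for the investigators.

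**What to change.** Before unmasking, amend VII.B as follows.

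- Name Boschloo's exact unconditional test, with the one-sided Fisher p-value as its statistic, one-sided at 5% as in VII.A, for the comparison of success rates.
- Keep Fisher's exact test as a supporting analysis, and state that the conclusion rests on Boschloo's test where the two differ.
- Call this the primary analysis only if the success rate is confirmed as the primary end point, since V.A currently names time to reduction in ulcer size.
- If Fisher's test is kept instead, state in VII.B that it is one-sided.

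The cost is one or two sentences, with no extra patients and standard software. There are two downsides. Boschloo's test is less well known to clinical readers, and the two tests will visibly disagree in exactly the tables that produce the gain, such as 5/15 vs 1/15. That is why the rule for disagreement has to be written down beforehand: a choice between the tests made after the results are seen would be selective.
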